4.2 Primary Objective

The primary objective is develop and test NeuViCare AI + care coach as an intervention for ED-to-community care transitions for PLWD and their care partners, offering a potential solution to the lack of existing ED care transition interventions.

4.3 Secondary Objectives (if applicable)

N/A

5 Study Design

5.1 General Design Description

Overall, we will use a sequential exploratory mixed-methods approach with integration of Specific Aims at the study design level. The rationale for the use of this approach is based on evidence that has shown the mixed-methods approach to be well-suited for the investigation of novel technology incorporation within healthcare settings by linking stakeholder's perspectives (qualitative) with implementation and patient-centered outcomes (quantitative). As performed by other user-centered design approaches, we will use a two-phase qualitative approach within Specific Aim 1, including: 1) semi-structured interviews with stakeholders, and 2) AI design optimization through a design thinking workshop. Specific Aim 2 will use a quantitative approach to assess implementation and patient-centered outcomes in a quantitative survey-based fashion.

5.1.1 Study Date Range and Duration

August 2022 – February 2024

5.1.2 Number of Study Sites

EDs at York St. Campus, Saint Raphael Campus, Shoreline Campus, and Bridgeport Campus

5.2 Outcome Variables

5.2.1 Primary Outcome Variables

After in-ED enrollment, we will collect baseline measurements of PLWD and their care partners. Particularly, at time 0 this will include domain assessments of validated tools addressing dementia knowledge, PLWD self-efficacy, psychological well-being, social connectedness, and caregiver experience. After ED- or hospital-community care transition, a virtual session led by the care coach will build upon discharge instructions by developing a comprehensive transdisciplinary care plan and integrating the use of NeuViCare AI technology. Subsequent sessions with the PLWD and their care partner will assess knowledge translation of NeuviCare AI, follow through with care plan, and the development of sustainable skills for preventing crisis and recidivism. At follow-up time points of 7 days, 30 days, and 3 months, participants will be contacted to reassess responses to above domains of interest (primary outcome).

5.2.2 Secondary and Exploratory Outcome Variables (if applicable)

Participants will be measured regarding their healthcare utilization, including ED visits, hospitalizations and care plan adherence with follow-up in the outpatient setting (secondary outcome). Finally, implementation outcomes of the NeuViCare AI technology will be

assessed through validated surveys of acceptability, appropriateness, feasibility, and usability (secondary outcome).

5.3 Study Population

For the older adult participants, the inclusion criteria will be: 1) age ≥ 65 years with a diagnosis of ADRD or dementia within the electronic health record OR new cognitive impairment identified during an ED visit, 2) be fluent in English or Spanish, 3) discharge to the community setting after an ED visit, and 4) be willing to engage in discussions regarding the implementation of a novel AI technology. Primary care partners of PLWD must possess a smart device (either a phone, tablet, or computer) that has internet access to utilize and interact with NeuViCare AI services.

5.3.1 Number of Participants

Phase 1 (qualitative interviews) – approximately 15

Phase 2 (Design Thinking Workshop) – approximately 15

Pilot Implementation – approximately 25

5.3.2 Eligibility Criteria/Vulnerable Populations

For the older adult participants, the inclusion criteria will be: 1) age ≥ 65 years with a diagnosis of ADRD or dementia within the electronic health record OR new cognitive impairment identified during an ED visit, 2) be fluent in English or Spanish, 3) discharge to the community setting after an ED visit, and 4) be willing to engage in discussions regarding the implementation of a novel AI technology. Primary care partners of PLWD must possess a smart device (either a phone, tablet, or computer) that has internet access to utilize and interact with NeuViCare AI services.

6 Methods

6.1 Treatment – Device

6.1.1 Intended Use for Device (provide the following information for each device being investigated in the study)

Building upon prior work in the outpatient Neurology setting, NeuViCare AI will include variations of its 5 components: 1) NeuViCare Planner - enables review of ordered tests and external resources recommended by the care provider; 2) NeuViCare Task-Support Service - provides context-sensitive, personalized SMS text-based assistance to help patients' complete care plan captured in the NeuViCare Planner; 3) NeuViCare Resource Advisor - presents trusted, unbiased advice to locate nearby resources listed within their care plan; 4) NeuViCare Advisor - educates and trains PLWD and their care partners at the moment of need; and 5) NeuViCare Community Hub - a safe virtual space which enables care partners to interact with other peer care partners to gain their experiential knowledge and emotional support.

6.1.2 Device Administration and Schedule

If interested and consented to joint the study, the PLWD and/or care partner will be given introductory instructions regarding the use of NeuViCare by the RA in the ED prior to discharge. Post-ED education will be performed by occupational therapy care coaches who will focus on incorporating NeuViCare AI technology to problem solve and build skills to empower PLWD and their care partners with knowledge and capacity to reduce severity of crisis escalations that result in healthcare utilization.

6.1.3 Method of Assignment/Randomization (if applicable)

N/A

6.1.4 Device Calibration

N/A

6.1.5 Storage Conditions

N/A

6.1.6 Concomitant therapy

N/A

6.1.7 Restrictions

There are no restrictions.

6.2 Assessments

6.2.1 Efficacy

Implementation outcomes of the NeuViCare AI technology will be assessed through validated surveys of acceptability, appropriateness, feasibility, and usability. *Acceptability* is defined as the perception that a given innovation is agreeable, palatable, or satisfactory. Acceptability will be measured by the Acceptability of Intervention Measure (AIM). *Appropriateness* is defined as the perceived fit, relevance, or compatibility of the innovation for a given setting or consumer, and/or perceived fit of the innovation to address a particular issue or problem. Appropriateness will be measured by the Intervention Appropriateness Measure (IAM). *Feasibility* is defined as the extent to which a new innovation can be successfully used or carried out within a given setting, and will be measured by the Feasibility of Intervention Measure (FIM). Finally, *usability* encapsulates several aspects including subjective assessments of effectiveness, efficiency, and satisfaction, and will be measured using the System Usability Scale (SUS). All measures identified are psychometrically valid and readable (Table).

Table 1: Implementation outcomes to be assessed	
Note: All responses will be scored on a 5-point Likert scale from 'Completely Disagree' to 'Completely Agree'.	
Acceptability of Intervention Measure (AIM)	
1.	NeuviCare AI meets my approval.
2.	NeuviCare AI is appealing to me.
3.	I like NeuviCare AI.
4.	I welcome NeuviCare AI.
Intervention Appropriateness Measure (IAM)	
5.	NeuviCare AI seems fitting.
6.	NeuviCare AI seems suitable.
7.	NeuviCare AI seems applicable.
8.	NeuviCare AI seems like a good match.
Feasibility of Intervention Measure (FIM)	
9.	NeuviCare AI seems implementable.
10.	NeuviCare AI seems possible.
11.	NeuviCare AI seems doable.
12.	NeuviCare AI seems easy to use.
System Usability Scale (SUS)	
13.	I think that I would like to use this system frequently.
14.	I found the system unnecessarily complex.
15.	I thought the system was easy to use.
16.	I think that I would need the support of a technical person to be able to use this system.
17.	I found the various functions in this system were well integrated.
18.	I thought there was too much inconsistency in this system.
19.	I would imagine that most people would learn to use this system very quickly.
20.	I found the system very awkward to use.
21.	I felt very confident using the system.
22.	I needed to learn a lot of things before I could get going with this system.

6.2.2 Safety

N/A

6.2.3 Adverse Events Definition and Reporting

The PI will take all possible measures to minimize any risks that may occur as a consequence of participation in this investigation. Adverse events will be recorded and noted by the PI, and reported to the Yale University Human Research Protection Program. While we feel that such events are very unlikely, we will follow all until resolution if adverse events occur.

6.2.4 Pharmacokinetics (if applicable)

N/A

6.2.5 Biomarkers (if applicable)

N/A

6.3 Study Procedures

6.3.1 Study Schedule

	2022-2023					
	July – Aug	Sep – Oct	Nov – Dec	Jan – Feb	Mar – Apr	May – June
Specific Aim 1						
Hire and train research assistants	X					
Phase 1 – Qualitative interviews	X	X				
Phase 2 – Design thinking workshop		X				
Adaptation of ED-specific NeuViCare AI			X			
Specific Aim 2						
In-ED enrollment for pilot implementation and testing				X	X	X
Data analysis						X
Manuscript preparation			X			X
Preparation of NIH/NIA K76, K23, or NIH STTR application					X	X
Dissemination of results at national meetings						X

6.3.2 Informed Consent

Both Specific Aims 1 and 2 will prospectively enroll participants identified and recruited by the trained Research Assistant (RA). For Specific Aim 1, the RA will be present in real-time within the ED and evaluate all ED older adults by electronic medical record screening. Those with identified dementia in the electronic medical record will be candidates for inclusion, among others described further below. Prior to participation the RA will then approach the treating clinician and ask for their approval to speak with the patient and caregiver prior to engagement. Informed consent will be obtained by personnel with up-to-date Yale HIC-required human subject's protection and HIPAA trainings. Written informed consent will be targeted, but verbal informed consent by telephone may need to be used given several present care partner/visitor restriction policies in the ED. Participants will be informed of the purpose of the study, the likely length of the qualitative interview or design thinking workshop, and the possible risks and benefits of participation. In addition, procedures to protect confidentiality will be reviewed. Participants will be reminded that inclusion is voluntary and that they are free to end the interaction at any point they wish. There will be no coercion or undue influence to participate in the research. The semi-structured interview guide will be developed, refined, and then reviewed and approved by the Yale University Human Research Protection Program prior to the start of the study, as will recruitment and written informed consent procedures.

Specifically, the RA will first assess the potential participant's capacity given that this work will prioritize PLWD and their care partners. The goal will be to determine their genuine comprehension of the study, not their mere ability to read and repeat the consent text. This will be completed by first approaching the candidate patient participant using the validated UBACC Capacity 10 questions. A score of ≥ 14 will be required to denote capacity, and a 'best response' will be required to be noted for at least one item in the domains of understanding, appreciation, reasoning and choice. For those without capacity, we will operate under the premise of 'obtaining assent and respecting dissent'. The RA will ask the patient if they agree to participate in the research. Assent can be expressed or indicated

verbally (e.g., saying “yes”), behaviorally (e.g., acting agreeably), or emotionally (e.g., having a positive facial expression). Furthermore, the separate assent form will be presented to the candidate patient participant, requesting their signature. Conversely, dissent will be noted by a ‘verbal or non-verbal indication of unwillingness to participate in study procedures. This will be noted and the participant will not be questioned further. When the patient lacks capacity but provides assent, the RA will then reach out by telephone to the contact listed in the electronic medical record to obtain proxy informed consent, going through the separate caregiver consent form. The relation of the contact will be described and reported in terms of family member (relation), designated care partner, legally authorized representative, surrogate decision maker to ensure they have authority to provide consent.

In the case of older adults with proxy-informed consent or among those that have capacity and also provided consent/assent, the RA will perform the 4AT. The 4AT is scored from 0-12 and tests for delirium and cognitive impairment. A score of ≥ 4 suggests possible delirium, with these people to be excluded from our study. A score of 1-3 suggests possible cognitive impairment. A score of 0 suggests delirium or severe cognitive impairment is unlikely. Additionally, the RA will then perform the AD8 with the older adult as well as their care partner by telephone. The AD8 is more focused on dementia specifically for screening. As a gold standard, a score of ≥ 2 on the care partner-completed AD8 will be noted to suggest cognitive impairment. In cases where AD8 scores differ between patient and care partner, the care partner score will be the one that dictates the ‘true’ AD8 score and therefore whether the patient is concerning for cognitive impairment or not.

For Specific Aim 2 (pilot testing), similar in-ED recruitment strategies will be used as above for identification, consent, cognitive screening, follow-up scheduling, and nominal gift card incentivization, but an additional method of recruitment will also be employed in this phase of the research. To broaden our potential participant pool (particularly when the RA is not in the ED), we will work with the JDAT team to obtain a Dashboard/list of ED patients that meet inclusion criteria. The JDAT team will query the electronic medical record to identify patients with a problem list diagnosis of ‘dementia’ that were discharged from the ED sites. The Dashboard/list of patients will be securely provided to the research team’s RA. The research team’s RA will then use EPIC In-Basket function to contact one of three clinicians with a recent and/or longitudinal relationship with the patient and/or caregiver, outside of the treating ED physician. Clinician #1 is the patient’s PCP, clinician #2 is the ED case manager, and clinician #3 is the ED follow-up nurse. The ED case manager, if involved in the patient’s care, has a longitudinal relationship that lasts up to 72 hours beyond emergency care, in which the patient or caregiver is able to contact them to address issues. In their current role, the ED follow-up nurse already contacts all patients >65 years of age discharged from the ED within 24-48 hours. If the enrolling RA is not present in the ED, the ED case manager or ED follow-up nurse during their interaction will briefly mention the study goals and inquire if the research team’s RA can contact them by telephone to further discuss the study. If for some reason, the case manager or follow-up nurse did not meet with a patient with dementia

identified through the JDAT Dashboard, then we will ask the patient's PCP through EPIC In-Basket if acceptable to contact the patient and caregiver. The research team's RA will then contact the patient and/or caregiver, first informing them that one of the 3 listed clinicians stated it was acceptable for the RA to contact them, followed then by describing the study, identifying interest, and consenting the patient and/or caregiver as described previously (similar to in-ED enrollment from here forward).

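### Do Aim 2 telephone recruits upset the app introduction and the timing of the 7-day, 30-day and 3-month surveys?

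*Combined protocol and SAP*

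**What the plan says.** Section 6.1.2 says that consented participants "will be given introductory instructions regarding the use of NeuViCare by the RA in the ED prior to discharge". The same section gives app education after the ED to the occupational therapy care coaches.

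Section 6.3.2 keeps in-ED recruitment for Aim 2 and adds a route for patients identified from the record after discharge. A clinician first agrees to, or arranges, the approach; the case manager or nurse, for example, asks whether the "RA can contact them by telephone to further discuss the study". The research assistant then telephones. Three kinds of clinician can open this route:

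- The nurse: the "follow-up nurse already contacts all patients >65 years of age discharged from the ED within 24-48 hours".
- The case manager, who "has a longitudinal relationship that lasts up to 72 hours beyond emergency care".
- As a fallback, the "PCP through EPIC In-Basket if acceptable to contact the patient and caregiver". No time is given for this one.

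After that, 6.3.2 refers back to the usual procedure: "consenting the patient and/or caregiver as described previously (similar to in-ED enrollment from here forward".

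On timing, 5.2.1 sets the baseline domain assessments at time 0 after in-ED enrolment, places the coach's virtual session "After ED- or hospital-community care transition", and continues: "At follow-up time points of 7 days, 30 days, and 3 months, participants will be contacted to reassess responses". It labels this reassessment the primary outcome. Sections 6.3.5 and 6.3.6 describe the three-month span as running from the ED visit, and 6.3.6 says so of the outcome surveys.

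Section 6.4.1 plans one kind of test, a paired t-test of baseline against 30-day scores on the DKAS and the Zarit scale. Everything else quantitative is descriptive or a mean set against a fixed cut-off. Section 6.4.2 gives no sample-size reasoning.

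**The concern.** Two things look out of joint for a participant enrolled by telephone.

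The first is delivery. A person who has already gone home cannot be introduced to the app in the ED, and 6.1.2 offers no other way.

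The second is the clock. For someone enrolled in the ED, the baseline date and the ED visit practically coincide, so the choice of origin is immaterial. For a telephone recruit it matters. Counted from the ED visit, the early surveys come sooner after baseline than their labels suggest. Counted from baseline, the last survey overshoots the limit in 6.3.6.

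The reassessments are the primary outcome, and a few days are a large share of seven. If sites used different origins, or if the ED visit were used throughout, 7-day scores from the two routes would reflect different times since baseline and would be pooled without comment. The 30-day change on the DKAS and Zarit could be touched in the same way, and a utilization window opened at the ED visit would take in events before enrolment.

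**Working it through.** The plan states no delay from ED visit to baseline, so there is no figure of its own to reproduce. The check asks what the contact times in 6.3.2 would imply under each origin.

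**Inputs**

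- Nurse contact at 24 to 48 hours and case manager access up to 72 hours (6.3.2).
- Survey points at 7 days, 30 days and 3 months (5.2.1). Three months is taken as 90 days.
- Assumption: baseline is taken on the day of the clinician's contact. The documents do not say this. The research assistant's call and consent come at or after that contact, so the true delay may be longer. The 72 hours is a period in which the family can reach the case manager, not a time to enrolment. The range is therefore illustrative and not a bound.

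**Formulas.** Delay d = hours / 24, so d = 1, 2 or 3 days.

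- Baseline origin: the baseline-to-survey intervals stay at 7 and 30 days. The 3-month survey falls on ED day 90 + d.
- ED-visit origin: the intervals become 7 − d and 30 − d, with relative losses d/7 and d/30.

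| d (days) | Baseline origin: loss at 7 and 30 days | Baseline origin: 3-month survey on ED day | ED-visit origin: baseline to 7-day survey | ED-visit origin: baseline to 30-day survey |
|---|---|---|---|---|
| 1 | 0 | 91 (1.1% over) | 6 days (14.3% shorter) | 29 days (3.3% shorter) |
| 2 | 0 | 92 (2.2% over) | 5 days (28.6% shorter) | 28 days (6.7% shorter) |
| 3 | 0 | 93 (3.3% over) | 4 days (42.9% shorter) | 27 days (10.0% shorter) |

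The primary care route has no stated delay. With assumed delays of 7 and 14 days, the ED-visit origin gives 7 − 7 = 0 and 7 − 14 = −7 days to the 7-day survey, so that survey would coincide with or precede baseline. It gives 30 − 7 = 23 and 30 − 14 = 16 days to the 30-day survey (23.3% and 46.7% shorter). Under the baseline origin the loss is again zero. An ED-visit origin thus gives an unworkable 7-day schedule for late recruits, which is a further reason not to read the plan that way.

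The split between routes is not given, so no pooled shift can be calculated. With a 3-day delay, the average shift at 30 days under the ED-visit origin lies anywhere from 0 days (no telephone recruits) to 3 days (all telephone recruits).

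**Which origin the text supports.** Section 5.2.1 names time 0, attaches it to the baseline, and lists the follow-up points as reassessments of the same domains. Sections 6.3.5 and 6.3.6 mention the ED visit only for the overall three-month span. No section ties the 7-day or 30-day survey to the ED visit.

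**Which analyses use the intervals.** Under 6.4.1 the only tested contrast is baseline against 30 days. No 7-day comparison is specified. The AIM, IAM and FIM means are set against 4 and the SUS against 68; neither cut-off depends on when follow-up began. ED visits and admissions are described, with no comparator.

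**App introduction.** Section 6.3.2 says that the in-ED steps apply in similar form after telephone consent. Section 6.1.2 has coaches teaching the app after the ED, and 5.2.1 has a virtual coach session that builds the app into the care plan. The app runs on the care partner's own device, and 6.3.6 has no in-person follow-up. Nothing in the introduction depends on being in the ED except the wording of 6.1.2.

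**The case for a change.** The strongest case for a change is that the natural reading is still only a reading. The baseline sentence in 5.2.1 is written for in-ED enrolment, so telephone recruits have no explicit time 0. Section 6.3.6 does tie the outcome surveys to the ED visit. The primary care route is open-ended. The carry-over clause points back to an introduction that was written for the ED, and no text hands that introduction to the coach. The outcome is labelled primary, and the repair would cost only a few sentences and two recorded items.

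Some of this stands. The sections do not agree word for word, and the documents give no delay, so a reader of the results would want to know each participant's route and days from ED visit to baseline. Those days follow from two dates that a study of this kind would ordinarily hold, the ED visit and the baseline survey, so they can be reported without a change to the plan.

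The rest does not carry to a conclusion. The argument that exposure differs by route treats time since baseline as exposure, yet the coach session has no fixed date for any participant, so coach exposure at day 7 is unspecified for in-ED recruits too. For utilization, either origin is a compromise: the ED visit brings in time before enrolment, and baseline covers a different period after the ED (days 3 to 33 against 0 to 30 with a 3-day delay). A descriptive count in one arm gains little from settling this in advance.

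**Conclusion.** No change to the plan follows. The mismatch is real but clerical: 6.1.2 is worded for one of the two enrolment routes, and 6.3.5 and 6.3.6 use the ED visit as shorthand for a start that 5.2.1 places at baseline. Analysts following 5.2.1 would count from baseline. The loss at 7 and 30 days is then zero, and the 3-month survey runs 1 to 3 days over (about 1% to 3% of 90 days) if baseline falls 24 to 72 hours after the ED visit.

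The larger figures, 14% to 43% at 7 days and 3% to 10% at 30 days, need an origin that no section states for those surveys, together with the assumed baseline date. The larger of the two ranges falls where no comparison is planned. Longer delays on the primary care route would matter only under that same origin.

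This rests on counting from baseline and on giving telephone recruits the introduction in a similar form, as 6.3.2 indicates. On that footing the 30-day paired comparison and the acceptability, appropriateness, feasibility and usability conclusions stand as planned. Aligning the wording would be tidy but would alter no planned result.
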